8.2.7 Important Protocol Deviations

An important protocol deviation (IPD) is a deviation that may significantly affect the completeness, accuracy, or reliability of the study data or that may significantly affect a subject's rights, safety, or well-being. A protocol deviation review team will categorize IPDs according to the protocol deviation plan during the study.

IPDs will be summarized descriptively based on the OL-FAS and presented by treatment group in parent studies and overall. Additionally, IPDs will be provided in an individual subject data listing.

8.3 Efficacy Analysis

8.3.1 Analysis of Primary Efficacy Endpoint

Not applicable since efficacy is not a primary objective.

8.3.2 Analysis of Secondary Efficacy Endpoint

8.3.2.1 Definition of Variables

Sweat chloride (SwCl): the SwCl value for a given visit will be calculated as the mean of the non-missing sweat chloride measurements obtained on the left and right arms at that visit. If one of the two arm measurements at a time point is missing, the other will be used as the mean. A volume ≥ 15 μL is required for an accurate determination of sweat chloride. Any results reported as having volume <15 μL will be considered missing. Any sweat chloride values reported as <10 mmol/L or >160 mmol/L will be considered missing.

Lung clearance index 2.5 (LCI_{2.5}): the LCI_{2.5} assessments are derived from N₂-multiple-breath washout (MBW) testing. Each MBW will be performed in multiple replicates for each visit and the final LCI_{2.5} value will be calculated from the technically acceptable washout replicates as graded and determined by a central reader. The following algorithm is used to derive the valid LCI_{2.5} value at each visit based on the multiple attempt replicates:

- When there is only one acceptable replicate at the visit, the LCI_{2.5} values will not be calculated. The assessment for that subject at the corresponding visit will be missing.
- When there are 2 or more acceptable replicates at the visit, the mean of the values for the acceptable replicates will be calculated as the LCI_{2.5} value at the corresponding visit.

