8 STATISTICAL ANALYSIS

8.1 General Considerations

The precision standards for reporting safety variables are provided in an internal Biometrics document that specifies the programming rules including the precision for derived variables.

The Schedule of Assessments is provided in Section 3 of CSP.

Continuous variables will be summarized using the following descriptive summary statistics: the number of subjects (n), mean, standard deviation (SD), median, minimum value (min), and maximum value (max).

Categorical variables will be summarized using counts and percentages. Percentages will be presented to 1 decimal place.

The **baseline value**, unless otherwise specified, for the long-term safety analysis will be the **TC safety baseline**, defined as the most recent non-missing measurement (scheduled or unscheduled) collected before the first dose of ELX/TEZ/IVA either in the parent study or the open label study, as applicable. The baseline value for the long-term efficacy analysis, unless otherwise specified, will be the **parent study baseline**, defined as the most recent non-missing measurement (scheduled or unscheduled) collected before the first dose of study drug in the parent study. For assessments collected in duplicate or triplicate, the baseline will be defined as the average of non-missing values.

Absolute change from baseline will be calculated as post-baseline value - baseline value.

Relative change from baseline will be calculated and expressed in percentage as $100\% \times (\text{Post-baseline value} - \text{Baseline value}) / \text{Baseline value}$.

Treatment-emergent (TE) Period will include the time from the first dose date of study drug in the OLE to 28 days after the last dose of the study drug in the OLE or to the date of completion of study participation (as defined in CSP Section 9.1.5), whichever occurs first.

Unscheduled visits: Unscheduled visit measurements will be included in analysis as follows:

- 1) In scheduled visit windows per specified visit windowing rules
- 2) In the derivation of baseline and last on-treatment measurements
- 3) In the derivation of maximum and minimum values during TE period, and maximum and minimum change from baseline values during TE period for safety analyses
- 4) In individual subject data listings as appropriate

Visit windowing rules: The analysis visit windows for protocol-defined visits are provided in [Appendix A](#).

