8.3.2.2 Analysis Method

Absolute change in SwCl from baseline:

The mixed-effects model for repeated measures (MMRM) for the parent study 116-FAS will be same as that described in the SAP for Study 116. In the MMRM for the OL-FAS, the absolute change from baseline in SwCl will be the dependent variable. The model will include treatment group (as randomized in the parent study), visit, and treatment-by-visit interaction as fixed effects, with continuous baseline LCI_{2.5} from the parent study and weight at Screening (<30 versus ≥30 kg) of the parent study as covariates.

The repeated-measures analysis will be based on the restricted maximum likelihood method assuming an unstructured covariance structure to model the within-subject errors. The denominator degrees of freedom will be based on the method proposed by Kenward-Roger⁶. If the model fails to converge due to the unstructured covariance assumption, a compound symmetry covariance structure will be used to model the within-subject errors. In the MMRM approach, assuming that the data are missing at random, no imputation of missing data will be performed.

Results from the 2 MMRMs (for the parent study and for the OE) will be presented in a single summary table. The number of subjects, least-squares means (LS means) for absolute change from baseline at scheduled visits within each treatment group (as randomized in the parent study) along with the corresponding standard error (SE), and 95% confidence interval (CI) will be presented. The LS means (±SE) for absolute change from baseline at each visit will also be plotted by treatment group (as randomized in the parent study).

In addition, the descriptive statistics for raw values and absolute changes from baseline by treatment group (as randomized in the parent study) and OL visit will be presented for the OL-FAS.

Absolute change in LCI_{2.5} from baseline:

Analysis of this endpoint will be based on an MMRM similar to the analysis of the absolute change from baseline in SwCl. A descriptive summary of raw values and absolute changes from baseline will also be presented.

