8.3.2.3 Sensitivity and Supportive Analysis of Secondary Endpoints

No sensitivity or supportive analysis is planned for the secondary endpoints.

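### Does setting sweat chloride results below 10 or above 160 mmol/L to missing distort the reported fall enough to need a change to the plan?

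*SAP*

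**What the plan says.** SAP 8.3.2.1 forms the visit value of sweat chloride (SwCl) as the mean of the two arms. If only one arm is usable: "If one of the two arm measurements at a time point is missing, the other will be used as the mean".

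Two exclusions follow. The first is for volume: "Any results reported as having volume <15 μL will be considered missing". Its reason is given in the sentence before it, which says that 15 μL is needed for an accurate result. The second is for the result itself: "Any sweat chloride values reported as <10 mmol/L or >160 mmol/L will be considered missing". It carries no volume condition and no reason. Protocol 11.2.1 gives no range or assay limit. It sends samples to a central laboratory for testing and interpretation, and leaves collection and processing details to separate instructions.

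SAP 8.3.2.2 analyses change from the parent-study baseline with an MMRM: "In the MMRM approach, assuming that the data are missing at random, no imputation of missing data will be performed". The model for the parent-study data "will be same as that described in the SAP for Study 116", and both sets of results go into one table. The section also plans "the descriptive statistics for raw values and absolute changes from baseline by treatment group" and visit, which under SAP 8.1 includes n, minimum and maximum. SAP 8.3.2.3 adds: "No sensitivity or supportive analysis is planned for the secondary endpoints".

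**The concern.** The range rule deletes an observation because of its own value. If an adequate-volume result of, say, 8 mmol/L is real, two things happen.

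- **Both arms low.** The visit is lost for a reason that depends on the lost value, which is not missing at random.
- **One arm low.** The visit stays in, but is represented by the higher arm alone.

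Both routes raise the on-treatment mean, so the fall in SwCl is understated. The planned tables would not show how much. They are computed after deletion, so no deleted result can appear in them, and n does not separate this cause of missingness from others. With no stated basis, no count and no sensitivity analysis, the rule looks unsupported on one of the two secondary endpoints.

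**Working it through.** The plan gives no SwCl mean, SD, effect size or removal rate, so there is no figure to reproduce. The check is of direction and size.

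**Inputs from the documents.** Limits 10 and 160 mmol/L; two arms per visit; seven post-baseline SwCl visits (Weeks 4, 8, 16, 24, 48, 72, 96; SAP Appendix A); about 108 subjects (SAP 6.2).

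**Assumptions.** On-treatment mean 30 to 50 and SD 15 to 20 mmol/L; gamma or lognormal shape; correlation 0.85 between arms and 0.3 or 0.7 between visits; even split of 108/2 = 54 per parent group.

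**Direction.** Let p be the share removed, K the mean of kept values and R the mean of removed values. The full mean is (1 − p)K + pR, so

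shift = K − full mean = p(K − R).

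For low removals K > R, so the shift is upward and the fall is understated. With R = 7 and K = 40, each 1% removed moves the mean by 0.01 × 33 = 0.33 mmol/L.

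**Truncation alone** (one measurement, no second arm, no use of other visits). Gamma with mean 40, SD 20 has shape 4 and scale 10.

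- P(X < 10) = 1 − e⁻¹(1 + 1 + 1/2 + 1/6) = 0.0190; P(X > 160) = 0.0001.
- Shares of the mean below 10 and above 160 (same formula with shape 5): 0.0037 and 0.0004.
- Kept mean = 40 × (1 − 0.0037 − 0.0004)/(1 − 0.0190 − 0.0001) = 40 × 0.9959/0.9809 = 40.61, a shift of 0.61.

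**With the second arm and the repeated-measures model.** Simulation of 20,000 subjects with Gaussian-copula dependence, the rule applied, and an unstructured-covariance maximum-likelihood fit. Bias is taken against the undeleted mean and averaged over visits. The SAP does not say whether the limits apply to each arm or to the visit mean, so both are shown (arm / visit). Gamma shape, mmol/L:

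| Mean / SD | Arm values removed | Truncation alone | Visit corr. 0.7 | Visit corr. 0.3 |
|---|---|---|---|---|
| 30 / 15 | 4.6% | 1.09 | 0.36 / 0.38 | 0.56 / 0.67 |
| 30 / 18 | 9.0% | 2.31 | 0.88 / 0.96 | 1.31 / 1.55 |
| 30 / 20 | 12% | 3.30 | 1.36 / 1.51 | 1.96 / 2.31 |
| 40 / 15 | 0.2% | 0.06 | 0.01 / 0.01 | 0.02 / 0.03 |
| 40 / 20 | 1.9% | 0.61 | 0.15 / 0.17 | 0.27 / 0.33 |
| 50 / 20 | 0.1% | 0.04 | 0.01 / 0.01 | 0.01 / 0.02 |

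Lognormal shapes give less at a mean of 30 (0.09 to 0.88) and practically nothing at 40 to 50 (−0.04 to 0). A normal shape gives more, about +2.3 to +2.6 at 30/18 with visit correlation 0.7. But 0.0478/0.1333 = 36% of its deleted tail is then below zero, which is impossible, so it is not a usable guide.

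**Yardsticks.** The standard error of one parent group's mean at a visit, ignoring the baseline contribution, is 15/√54 = 2.04 to 20/√54 = 2.72. The largest entry, 2.31 at SD 20, compares with 2.72. If baseline is assumed to be 100, the fall at a mean of 30 is 70, and 2.31/70 is about 3% of it. At 40/20 it is at most 0.33/60, about 0.6%.

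**Upper limit.** The chance of a baseline result above 160 is 0.00003 at an assumed mean 100, SD 15, and 0.003 at 105, SD 20. The latter is 0.003 × 108 = 0.3 subjects. It can be ignored.

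**The case for a change.** The best case for a change is this. The rule removes data by value, the model assumes missing at random, and no planned output reveals how much was removed. A minimum well above 10 would reassure, but a minimum near 10 would fit a wide range of bias. The remedy looks cheap: one sentence on the basis of the limits, a count of removals, and perhaps an extra model run that keeps the values.

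The factual part stands. The basis is unstated, the level is not spelled out, and deletion of genuine values would not be missing at random. At a low mean with a wide SD the effect is also more than trivial.

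The step from there to a change does not stand.

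- **The harm is conditional.** It needs results below 10 to be real, and nothing in the documents says so. The range rule directly follows the volume rule and, like it, refers to results as reported, which points to a data-quality screen. If so, keeping the values would add error.
- **The level is filled in sensibly.** The SAP calls the visit mean calculated and applies both exclusions to what is reported, which fits laboratory results per arm. In the table the two readings differ by at most 2.31 − 1.96 = 0.35.
- **The additions change no planned result.** The rule would remain the main analysis. If the laboratory reports only that a result is below 10, an extra run that sets it to 10 recovers only part of any bias: about 0.3 of 0.8 to 0.9 would remain for gamma 30/18 at visit correlation 0.7.
- **A count trigger would be arbitrary.** Gamma 40/20 removes 1.9% of arm values, yet its arm-level bias runs from 0.15 to 0.27 depending only on the visit correlation.

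**Conclusion.** No change is needed. This is missing explanatory detail around an objective, prespecified, two-sided rule. If the limits mark assay validity there is no bias at all. If low results are genuine, the fall in SwCl is understated, which works against the treatment. For non-negative shapes the amount is about 0 to 0.3 mmol/L at on-treatment means of 40 to 50. At a mean of 30 it is about 0.1 to 1.6 for SDs of 15 to 18, and about 0.4 to 2.3 at SD 20. An SD above 20 at that mean would give more. These figures rest on assumed means, SDs, shapes and correlations, because the documents supply none.

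The endpoint is secondary, is reported as LS means with confidence intervals within parent groups, and has no hypothesis test described. The safety objective does not depend on it. A sentence in the study report giving the basis of the limits and the number of results removed would help readers, but the planned analysis would be the same with or without it.

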8.3.2.2 Analysis Method

Absolute change in SwCl from baseline:

The mixed-effects model for repeated measures (MMRM) for the parent study 116-FAS will be same as that described in the SAP for Study 116. In the MMRM for the OL-FAS, the absolute change from baseline in SwCl will be the dependent variable. The model will include treatment group (as randomized in the parent study), visit, and treatment-by-visit interaction as fixed effects, with continuous baseline LCI_{2.5} from the parent study and weight at Screening (<30 versus ≥30 kg) of the parent study as covariates.

The repeated-measures analysis will be based on the restricted maximum likelihood method assuming an unstructured covariance structure to model the within-subject errors. The denominator degrees of freedom will be based on the method proposed by Kenward-Roger⁶. If the model fails to converge due to the unstructured covariance assumption, a compound symmetry covariance structure will be used to model the within-subject errors. In the MMRM approach, assuming that the data are missing at random, no imputation of missing data will be performed.

Results from the 2 MMRMs (for the parent study and for the OE) will be presented in a single summary table. The number of subjects, least-squares means (LS means) for absolute change from baseline at scheduled visits within each treatment group (as randomized in the parent study) along with the corresponding standard error (SE), and 95% confidence interval (CI) will be presented. The LS means (±SE) for absolute change from baseline at each visit will also be plotted by treatment group (as randomized in the parent study).

In addition, the descriptive statistics for raw values and absolute changes from baseline by treatment group (as randomized in the parent study) and OL visit will be presented for the OL-FAS.

Absolute change in LCI_{2.5} from baseline:

Analysis of this endpoint will be based on an MMRM similar to the analysis of the absolute change from baseline in SwCl. A descriptive summary of raw values and absolute changes from baseline will also be presented.

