12.3.3.2 Analysis of Secondary Efficacy and Pharmacodynamic Endpoints

The Secondary Endpoints include:

- **Absolute change from baseline in SwCl**

The analysis of this endpoint will be performed using a mixed-effects model for repeated measures (MMRM) with absolute change from baseline in SwCl at each post-baseline visit in this current open-label study as the dependent variable. The model will include the parent study treatment group, visit, and parent study treatment-by-visit interaction as fixed effects, and will be adjusted for main covariates as appropriate. The least squares (LS) mean estimate with a 2-sided 95% CI at each visit will be provided.

- **Absolute change from baseline in LCI_{2.5}**

Analysis of this efficacy endpoint will be based on a MMRM model similar to the analysis of the absolute change from baseline in SwCl.

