12.3.3.3 Analysis of Other Efficacy and Pharmacodynamic Endpoints

Other Endpoints include:

- **Absolute change from baseline in ppFEV₁**

Analysis of this variable will be based on an MMRM model similar to the analysis of the absolute change from baseline in LCI_{2.5}.

- **Absolute change from baseline in CFQ-R respiratory domain score**

Analysis of this variable will be based on an MMRM model similar to the analysis of the absolute change from baseline in LCI_{2.5}.

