8.2.2 Demographics and Baseline Characteristics

Demographics and baseline characteristics will be summarized based on the OL-FAS and presented by treatment group in the parent study and overall.

Demographic data from the parent study (445-116) will include the following:

- Age at parent study baseline (in years)
- Sex (female and male)
- Ethnicity (Hispanic or Latino, not Hispanic or Latino, and not collected per local regulations)
- Race (White, Black or African American, Asian, American Indian or Alaska Native, Native Hawaiian or Other Pacific Islander, multiracial, and not collected per local regulations)
- Country

Baseline characteristics from the parent study (445-116) will include the following:

- Weight (kg)
- Weight-for-age z-score
- Height (cm)
- Height-for-age z-score
- BMI (kg/m²)
- BMI-for-age z-score

Stratification categories used in the parent study will include the following:

- LCI_{2.5} at Screening Visit (<10, ≥10)
- Weight at Screening Visit (<30, ≥30 kg)

Disease characteristics from the parent study (445-116) baseline will include the following:

- Sweat chloride at parent study baseline (continuous)
- LCI_{2.5} at parent study baseline (continuous)
- ppFEV₁ category at parent study baseline (<70, ≥70 to ≤90, and >90)
- ppFEV₁ at parent study baseline (continuous)

- CFQ-R respiratory domain score at parent study baseline (child 6-11's version, continuous)
- Prior use of dornase alfa (Yes, No)
- Prior use of azithromycin (Yes, No)
- Prior use of inhaled antibiotic (Yes, No)
- Prior use of any bronchodilator (Yes, No)
- Prior use of any inhaled bronchodilator (Yes, No)
- Prior use of any inhaled hypertonic saline (Yes, No)
- Prior use of any inhaled corticosteroids (Yes, No)

Prior medication use definition is same as that for the baseline characteristics summary presented in the parent studies. In addition, data listings will also be provided for:

- Informed consent
- Inclusion/Exclusion criteria violation for subjects with any such violations

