8.3.3.2 Analysis Method

Absolute change in ppFEV₁ from baseline:

Analysis of this endpoint will be based on an MMRM similar to the analysis of the absolute change in SwCl. A descriptive summary of raw values and absolute changes from parent study baseline will also be presented.

The primary analysis will use the spirometry data obtained at clinic only. An additional analysis may be performed to include all available spirometry data obtained at clinic and obtained at home, if the spirometry data obtained at home are assessed to be reasonably consistent with the spirometry data obtained at clinic.

Absolute change in CFQ-R respiratory domain (RD) score from baseline:

Analysis of this endpoint will be based on an MMRM similar to the analysis of the absolute change in SwCl. A descriptive summary of raw values and absolute changes from parent study baseline will also be presented. In addition, the descriptive summary for raw values and the absolute change from parent study baseline of the parent version's CFQ-R RD score will be presented.

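### The open-label sweat chloride MMRM leaves out baseline sweat chloride, and the plan does not settle whether the ppFEV1 and CFQ-R models use their own baseline: a minor loss of efficiency

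*SAP*

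**What the plan says.** SAP 8.3.2.2 gives the open-label SwCl model in full: change from parent-study baseline as the outcome; randomised parent group, visit and their interaction as fixed effects; and adjustment "with continuous baseline LCI_{2.5} from the parent study and weight at Screening", weight being split at 30 kg. Baseline SwCl is not listed, though SAP 8.2.2 summarises it ("Sweat chloride at parent study baseline (continuous"). The same section gives the parent stratification factors: screening weight group and "LCI_{2.5} at Screening Visit (<10, ≥10". The two covariates correspond to these factors, with LCI2.5 entered as a continuous baseline value.

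The other models are defined by reference. SAP 8.3.2.2 makes the LCI2.5 model similar to the SwCl model. For ppFEV1 and CFQ-R, SAP 8.3.3.2 says: "Analysis of this endpoint will be based on an MMRM similar to the analysis of the absolute change in SwCl". Protocol 12.3.3.3 ties both to a different model, an "MMRM model similar to the analysis of the absolute change from baseline in LCI_{2.5", and Protocol 12.3.3.2 refers that one back to SwCl: "Analysis of this efficacy endpoint will be based on a MMRM model similar to the analysis of the absolute change from baseline in SwCl". The protocol leaves the choice of covariates open.

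The reported results are LS means by parent group and visit with SE and 95% CI, tabulated together with the Study 116 model and plotted. The SAP also plans "the descriptive statistics for raw values and absolute changes from baseline by treatment group". SAP 8.3.2.3 plans no sensitivity or supportive analysis for the secondary endpoints.

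**The concern.** In a change-score model, own baseline is usually the strongest available predictor. It costs no subject here, because a subject without a baseline has no change score. Without it, chance baseline differences between the two parent groups stay in the plotted SwCl curves, and the LS means are less precise than the collected data allow. LCI2.5 is the one endpoint whose own baseline is certainly in its model, so the endpoints may be adjusted on different footings.

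For ppFEV1 and CFQ-R, two programmers could build different models from the same text. One would carry over exactly the two SwCl covariates. The other would follow the protocol's link to the LCI2.5 model and give each endpoint its own baseline.

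**Working it through.** The plan has no figure to reproduce. SAP 6.2 gives only the expected enrolment of about 108, with no SD, correlation or precision target.

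**Inputs.** All but the 108 are assumptions:
- 54 subjects per parent group (108/2).
- Baseline SD set to 1; on-treatment SD k = 0.7, 1 or 1.3.
- Correlation r = 0.3, 0.5 or 0.7 between own baseline and on-treatment value.
- Correlation q = 0, 0.3 or 0.5 between baseline LCI2.5 and own baseline. LCI2.5 is taken to predict the on-treatment value only through own baseline.
- One visit, complete data, weight group ignored, LS means evaluated at the pooled baseline mean.

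**Formulas** (variance per subject; divide by 54 for the squared SE of a group LS mean):
- Own baseline absent, q = 0: U = 1 + k² − 2rk
- Residual variance with own baseline, which sets the printed SE: M = k²(1 − r²)
- True variance of the adjusted LS mean: A = M + (1 − rk)²/2. The second term arises because the pooled baseline mean also varies between samples.
- Fall in true SE = 1 − √(A/U); fall in printed SE = 1 − √(M/U)
- Coverage for the population mean change = 2Φ(1.96√(M/A)) − 1

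**Example, r = 0.5, k = 1.** U = 1 + 1 − 1 = 1; M = 0.75; A = 0.75 + 0.25/2 = 0.875. The true SE falls by 1 − √0.875 = 6.5%, the printed SE by 1 − √0.75 = 13.4%. Coverage is 2Φ(1.96 × √(0.75/0.875)) − 1 = 93.0%.

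| k | r | U | M | A | True SE falls | Printed SE falls | Coverage |
|---|---|---|---|---|---|---|---|
| 0.7 | 0.3 | 1.070 | 0.446 | 0.758 | 15.8% | 35.4% | 86.7% |
| 0.7 | 0.5 | 0.790 | 0.368 | 0.579 | 14.4% | 31.8% | 88.2% |
| 0.7 | 0.7 | 0.510 | 0.250 | 0.380 | 13.7% | 30.0% | 88.8% |
| 1 | 0.3 | 1.400 | 0.910 | 1.155 | 9.2% | 19.4% | 91.8% |
| 1 | 0.5 | 1.000 | 0.750 | 0.875 | 6.5% | 13.4% | 93.0% |
| 1 | 0.7 | 0.600 | 0.510 | 0.555 | 3.8% | 7.8% | 94.0% |
| 1.3 | 0.3 | 1.910 | 1.538 | 1.724 | 5.0% | 10.3% | 93.6% |
| 1.3 | 0.5 | 1.390 | 1.268 | 1.329 | 2.2% | 4.5% | 94.4% |
| 1.3 | 0.7 | 0.870 | 0.862 | 0.866 | 0.2% | 0.5% | 94.9% |

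The gain disappears as rk approaches 1.

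**Allowing for the planned LCI2.5 covariate.** The true variance under the plan becomes P = (1 − rk)²(1 − q²/2) + M. At r = 0.5, with q = 0.3 or 0.5:
- k = 0.7: P = 0.771 or 0.737 against A = 0.579; true SE falls 13.4% or 11.4%.
- k = 1: P = 0.989 or 0.969 against 0.875; 5.9% or 5.0%.
- k = 1.3: P = 1.384 or 1.375 against 1.329; 2.0% or 1.7%.

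**Coverage under the plan.** The planned model's own variance is (1 − rk)²(1 − q²) + M. At r = q = 0.5 its 95% CI covers 94.1% (k = 0.7), 94.6% (k = 1) and 94.9% (k = 1.3).

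**Chance gap between the curves that adjustment removes** (q = 0): SD |1 − rk|√(2/54), from 0.017 to 0.152 baseline SDs.

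**Simulation.** With 20,000 runs at 54 per group, adjusted/unadjusted true SE ratios for r = 0.3/0.5/0.7 were 0.849/0.858/0.864 (k = 0.7), 0.908/0.936/0.961 (k = 1) and 0.955/0.980/1.001 (k = 1.3), in line with the table. Adjusted coverage ran from 86.8% to 95.2%; unadjusted coverage was 94.9% to 95.3%. A separate simulation at k = 1 (4,000 runs, complete data) found both estimators unbiased.

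**The case against.** The strongest reply is that the planned intervals are close to nominal and the adjusted ones would not be. About half of the visible narrowing is not true precision, and the largest gains (k = 0.7) go with the poorest coverage. This stands as a cost to state. It is not a reason to keep the omission: it is the usual conditional property of covariate-adjusted LS means, the planned LCI2.5 model already has it, and the unadjusted summaries remain.

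Second, the covariates may be inherited. They correspond to the parent stratification factors, the protocol synopsis says efficacy methods will resemble those of the parent study, and SAP 8.3.2.2 puts both studies' LS means in one table. The Study 116 SAP is not among the documents, so whether the change would align that table or split it cannot be checked. This stands, and the fix has to cover the table.

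Third, a reader might infer that ppFEV1 and CFQ-R are certainly modelled without their own baselines. The documents do not support that. *Similar* is not *identical*, and the protocol links both endpoints to the LCI2.5 model, which does contain its own baseline.

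Fourth, SAP 8.2.2 already presents the baselines by parent group, so an imbalance would be visible. That is true, but visibility does not adjust the LS means.

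**Conclusion.** The omission is certain for SwCl. For ppFEV1 and CFQ-R the plan is ambiguous, not shown to be deficient. The point is minor: these are secondary and other endpoints of a study whose primary objective is safety.

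Under the stated assumptions, own baseline would lower the true SE of by-group LS means by about 0 to 16%. At r = 0.5, with LCI2.5 already in the model and correlated 0.3 to 0.5 with own baseline, the range is about 2 to 13%. At k = 1.3 the fall is 5% or less, and almost nothing at r = 0.7.

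A reader might infer that the planned SwCl estimates are biased, or that a comparison of the parent groups is compromised. Neither follows: complete-data within-group means are unbiased, and no between-group test is planned. The check covers one visit with complete data. It does not address dropout that depends on own baseline.

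**What to change.** Before database lock, by the amendment route in SAP section 3:

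1. In SAP 8.3.2.2, add continuous parent-study baseline SwCl to the SwCl model. Leave the LCI2.5 model as it is.
2. In SAP 8.3.3.2, state that the ppFEV1 and CFQ-R respiratory domain models each include their own continuous parent-study baseline, in addition to baseline LCI2.5 and screening weight group.
3. Evaluate LS means at the pooled OL-FAS baseline mean.
4. In the joint Study 116 and open-label table and in the plot, footnote the covariates of each model. If the Study 116 model lacks own baseline, say that the two sets of LS means are adjusted differently.
5. Note that the model-based CIs are conditional on observed baselines and too narrow for the population mean change. Show the planned unadjusted changes beside the LS means. SAP 8.1 specifies "the number of subjects (n), mean, standard deviation (SD), median, minimum value (min), and maximum value (max" for these, so a reader can form an unconditional interval. That interval uses observed cases only, so with missing data it does not estimate quite the same quantity as the MMRM.

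The cost is SAP wording and at most one added covariate in each of three models, with negligible degrees of freedom at about 108 subjects and no subject lost. The real downside is coverage of about 87 to 95% for the population mean change, against about 94 to 95% under the planned model.
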